**ARM A (n=20; Arm will close to enrollment once 10 participants have completed study visits):**

**Visit 1 (screening):** Eligible MSM will be questioned about their medical history, undergo an HIV test, and a peripheral blood sample for creatinine and hepatitis B testing, as well as testing for baseline levels of study drug. A physical exam may also be completed. Participants will then be asked to return within 1-6 weeks for visit 2.

**Visit 2:** Participants will return to the clinic to be given their first dose of 2 pills of TDF/FTC with instructions to take the next pill 24 hours later, and document that dose with a time-stamped photograph or video.

**Visit 3:** Participants will return to the clinic 48 hours after first dose, and 24 hours after second dose to receive their third and final dose of one pill. After the dose is taken, approximately 24mL of blood will be drawn, urine sample, and a finger stick will be collected.

**Visit 4:** Participants will return to the clinic 24 (+/- 2 hrs) hours after their last dose at Visit 3. Approximately 24mL of blood will be drawn, urine sample, and a finger stick will be collected.

**Visit 5:** Participants will return to the clinic 2-5 days after their last dose at Visit 3. Approximately 24mL of blood will be drawn, urine sample, and a finger stick will be collected.

**Visit 6:** Participants will return to the clinic 7 (+/- 1 day) days after their last dose at Visit 3. Approximately 24mL of blood will be drawn, urine sample, and a finger stick will be collected.

**Visit 7:** Participants will return to the clinic 14 days (+/- 1 day) after their last dose at Visit 3. Approximately 24mL of blood will be drawn, urine sample, and a finger stick will be collected.

**Visit 8:** Participants will return to the clinic 21 (+/- 1 day) days after their last dose at Visit 3. Approximately 24mL of blood will be drawn, urine sample, and a finger stick will be collected.

**Visit 9:** Participants will return to the clinic 28 days (+/- 1 day) after their last dose at Visit 3. Approximately 24mL of blood will be drawn, urine sample, and a finger stick will be collected, along with hair sample. This visit will also include urine and rectal STI screening.

**ARM B (n=20; arm will close to enrollment once 10 people have completed study visits)**

**Visit 1 (screening):** Eligible MSM will be questioned about their medical history, undergo an HIV test, and a peripheral blood sample for creatinine and hepatitis B testing, as well as testing for baseline levels of study drug. A physical exam may also be completed. Participants will then be asked to return within 1-6 weeks for visit 2.

**Visit 2:** Participants will return to the clinic to receive their first set of study drug for weekly 2-1-1 dosing. The first dose of 2 pills will be taken in clinic, the next dose of 1 pill to be taken 24 hours later at home, and the last dose at home 48 hours from the first dose (24 hours after the second dose). Participants will be instructed to take their 2-1-1 dosing on the same days every week. Participants will be instructed to provide documentation of all other dosing with a time-stamped video or picture.

**Visits 3-14:** Participants will return after finishing their weekly 2-1-1 dose, to do their weekly convenience sampling. Approximately 24 mL of blood will be drawn, urine sample, and a finger stick will be collected. An HIV test will be completed at visits 6, 10 and 14 (once per month) along with hair samples. Urine and rectal STI screenings will be conducted at visit 10. An additional creatinine test will be done at visit 14. Participants will be provided with their medication at visits 5, 8, and 11.

**Visit 15:** Participants will return to the clinic to take their final dose of study drug in clinic. After the dose is taken, approximately 24mL of blood will be drawn, urine sample, and a finger stick will be collected.

**Visit 16:** Participants will return to the clinic 24 (+/- 2 hrs) hours after their last dose at Visit 15. Approximately 24mL of blood will be drawn, urine sample, and a finger stick will be collected.

**Visit 17:** Participants will return to the clinic 2-5 days after their last dose at Visit 15. Approximately 24mL of blood will be drawn, urine sample, and a finger stick will be collected.

**Visit 18:** Participants will return to the clinic 7 (+/- 1 day) days after their last dose at Visit 15. Approximately 24mL of blood will be drawn, urine sample, and a finger stick will be collected.

**Visit 19:** Participants will return to the clinic 14 days (+/- 1 day) after their last dose at Visit 15. Approximately 24mL of blood will be drawn, urine sample, and a finger stick will be collected.

**Visit 20:** Participants will return to the clinic 21 (+/- 1 day) days after their last dose at Visit 15. Approximately 24mL of blood will be drawn, urine sample, and a finger stick will be collected.

**Visit 21:** Participants will return to the clinic 28 days (+/- 1 day) after their last dose at Visit 15. Approximately 24mL of blood will be drawn, urine sample, and a finger stick will be collected, along with a hair sample.

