### Study visits

When possible, study activities such as questionnaires will be done remotely due to the ongoing COVID-19 pandemic.

Eligible subjects will be sequentially assigned to study arms: A, B, C & D. Our goal is to have 10 participants complete each arm.

Participants may participate in more than one study arm; however, at least 8 weeks must lapse after completion of one study arm, before entry into another. Participants who participate in more than one arm do not have to repeat the screening visit (visit 1) when starting another arm; they will begin the new arm at visit 2. However, they will be re-consented on the consent form of the new arm prior to any arm-specific study activities being performed.

Participants who are unable to donate hair will not be considered protocol deviations.

The consent process will be conducted in a private exam room at the Hope Clinic or electronically via an online e-consent platform. Copies of the consent form for this project will not be placed in individuals' medical records since this study collects sensitive information such as HIV status and sexual orientation. All participants will be provided a copy of the signed informed consent form (ICF).

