Primary study outcome: Median (range) TFV-DP concentrations in dried blood spots will be measured at Visit 4 in Arm A and compared to TFV-DP concentrations in dried blood spots measured at Visit 16 in Arm B to compare accumulation of drug following weekly ED-PrEP dosing. In addition, TFV-DP concentrations in dried blood spots will be measured at Visit 16 in Arm C and compared to TFV-DP concentrations in dried blood spots measured at Visit 16 in Arm D to compare accumulation of drug following the different ED-PrEP dosing strategies. Differences in median drug concentrations between arms will be analyzed with a non-parametric Wilcoxon-signed rank tests and a p-value <0.05 will be considered significant.

Other drug level outcomes will be exploratory.

Future use of specimens

Leftover biologic specimens will be stored and used for future research use at Emory University Hope Clinic or the CDC. Stored samples will only be distributed to researchers who have obtained protocol approval from an IRB (or appropriate waiver).

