### **Arm A (closed as of 7/14/21)**

Participants will receive \$20 for the screening visit, \$20 for each study visit involving sampling procedures, to compensate for time and effort. If participants do not finish the study, we will compensate for the visits they have completed (\$180 total for those who finish all study visits). Participants who complete all 9 study visits for Arm A will receive a \$50 “finishing bonus” at their last visit, to improve retention in this arm.

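### Timing Arm B's Visit 3 at 24 hours would give each participant a single-course reference for accumulation, at little cost

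*Combined protocol and SAP*

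**What the plan says.** - **Primary contrast** (Statistical Analysis Plan, primary study outcome): dried-blood-spot TFV-DP "will be measured at Visit 4 in Arm A and compared to TFV-DP concentrations in dried blood spots measured at Visit 16 in Arm B". Its stated purpose is to compare accumulation after weekly dosing.
- **Test** (same paragraph): "Differences in median drug concentrations between arms will be analyzed with a non-parametric Wilcoxon-signed rank tests", and "a p-value <0.05 will be considered significant". For everything else, "Other drug level outcomes will be exploratory". No contrast of a participant's later level with their own first-course level is planned.
- **Arm A, Visit 4:** "Participants will return to the clinic 24 (+/- 2 hrs) hours after their last dose at Visit 3". Arm B Visit 16 has the same window after the dose taken at Visit 15.
- **Arm B, Visits 3-14:** "Participants will return after finishing their weekly 2-1-1 dose, to do their weekly convenience sampling". No hour or day window is given. In the first course the two-pill dose is taken in clinic, and the second and third doses are taken at home, 24 and 48 h later. Dosing falls on the same days each week, and home doses are documented by time-stamped picture or video.
- **Arms and size** (Study visits): assignment is sequential, with no mention of randomisation. A person may enter a second arm after at least 8 weeks. "Our goal is to have 10 participants complete each arm".
- **Status of Arm A** (Compensation): "Arm A (closed as of 7/14/21".

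**The concern.** At Visit 3 an Arm B participant has had the same exposure as an Arm A participant at Visit 4: one 2-1-1 course. If that sample were taken at the same time after the last dose as Visit 16, the ratio of the two would estimate accumulation in that person. As written, Visit 3 is one of twelve loosely scheduled weekly draws, and the SAP makes no use of it for this purpose.

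The only planned accumulation estimate is therefore the difference between two small, non-randomised groups. Any difference between those groups in the factors that govern drug level passes straight into it. A sample already being collected could supply an estimate free of that component, but without a time window it does so only with a blur. A draw time, once past, can be recorded or adjusted for but not changed.

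**Working it through.** The documents give no SD, effect size, half-life or power, so there is no planned figure to reproduce. The half-life, log-SD and within-person correlation below are assumptions, shown as ranges where the result is sensitive to them.

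**1. When Visit 3 can fall.** The third pill is at 48 h of a weekly cycle of 7 × 24 = 168 h. The next course starts 168 − 48 = 120 h later. Visit 3 can thus fall about 0 to 120 h after the third pill, against 22 to 26 h at Arm A Visit 4 and Arm B Visit 16.

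**2. Effect of a late draw.** Assume first-order decay with half-life h days. The level at 120 h relative to 24 h (4 days later) is 2^(−4/h).

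| h (days) | 120 h / 24 h | Fall | Overstatement of Visit 16/Visit 3 |
|---|---|---|---|
| 10 | 0.758 | 24% | 1/0.758 = 1.32, or 32% |
| 21 | 0.876 | 12% | 1/0.876 = 1.14, or 14% |

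These are the extremes for the latest possible draw. By contrast, the whole 22 to 26 h window moves the level by about 1% at h = 10: 2^(−(4/24)/10) = 0.989.

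**3. Size of the accumulation being estimated.** Visits 2 to 15 imply 13 weekly courses. With superposition, the ratio of Visit 16 to a single course at the same time after dose is (1 − q^13)/(1 − q), where q = 2^(−7/h).
- h = 10: q = 0.616, ratio 2.60.
- h = 21: q = 0.794, ratio 4.61.

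**4. Precision of the two estimates.** Assume log-scale SD 0.4 and n = 10 (10 per arm between arms; 10 pairs within person), with t quantiles.
- Between arms: SE = 0.4 × √(2/10) = 0.179. With 18 df, t = 2.101, the half-width is 0.376 and the limits are ×/÷1.46.
- Within person, correlation 0.5: SE = 0.4 × √(2 × 0.5/10) = 0.126. With 9 df, t = 2.262, the half-width is 0.286 and the limits are ×/÷1.33.
- Within person, correlation 0.8: SE = 0.4 × √(2 × 0.2/10) = 0.080. The half-width is 0.181 and the limits are ×/÷1.20.

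The log-scale half-width falls by 24% (1 − 0.286/0.376) to 52% (1 − 0.181/0.376). The gain disappears only if the correlation is below about 1 − (2.101/2.262)² = 0.14.

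**5. Is the planned comparison short of power?** Not at these ratios. At 2.60 the standardised difference is ln 2.60/0.179 = 0.956/0.179 = 5.3, which gives power of about 99.9%. The lower 95% limit would be about 2.60/1.46 = 1.8.

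**The case against.** The strongest reply is that A versus B already does its job. The study's goal is to learn whether a biomarker can validate self-reported dosing. That depends on how levels are distributed between people under each pattern, which two separate groups supply. At the accumulation in step 3 the planned test would almost certainly be significant. Much of the timing blur can also be recovered: home doses are time-stamped, and Arm A Visits 4-9 trace the single-course decline from 24 h to 28 days. All of this stands. It makes the within-person ratio a supporting estimate, not a replacement.

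Several stronger readings are tempting but not supported:
- **That the loose Visit 3 is why accumulation is read between arms.** The SAP fixes that contrast, and it would be the same with a timed Visit 3.
- **That Arms A and B hold different people.** Entry into a second arm is allowed. The overlap is unknown, and the SAP does not say how it would be handled.
- **That Arm B ran later, so that conduct or assay changes separate the arms.** The closure date fits the rule that Arm A closes after 10 completers. The documents give no enrolment dates for Arm B, so non-concurrency would be conjecture.
- **That Arms C and D need the same change.** Their primary comparison is C against D at Visit 16 and uses no single-course reference.

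The within-person ratio has limits of its own. Thirteen weekly courses put about 12 weeks between its two samples, so assay or conduct drift over that time remains. The third pill of the first course is taken at home, whereas the Visit 16 sample follows a dose taken in clinic. Up to three missed visits are tolerated, and nothing protects Visit 3.

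**Conclusion.** The point holds as a worthwhile, inexpensive improvement. Arm B collects a sample after exactly one course but does not time it to match Visit 16, and no within-participant accumulation estimate is planned. A matched Visit 3 would remove between-group differences from a supporting estimate. It would narrow the 95% limits from ×/÷1.46 to between ×/÷1.20 and ×/÷1.33, if the log-SD is 0.4 and the within-person correlation is 0.5 to 0.8 with 10 participants. Left untimed, a draw at the 120 h extreme would bias the ratio upward by 14 to 32%, if the half-life is 10 to 21 days. None of these inputs is in the documents. No stated figure is wrong, and the A versus B comparison is not invalidated.

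**What to change.** 1. **Visit 3, Arm B only.** For participants not yet past it, schedule the sample 24 (± 2) h after the third pill of the first course. That is 48 + 24 = 72 h after the first dose at Visit 2, the same interval that Arm A already follows from Visit 2 to Visit 4. Leave Visits 4-14 and the dosing schedule unchanged. Ask staff to treat Visit 3 as one not to miss.
2. **Participants already past Visit 3.** Derive time since last dose from the time-stamped dose record and the draw time (assumed to be recorded). Report it with the ratio. As a sensitivity analysis, adjust the Visit 3 value to 24 h using the Arm A decline.
3. **SAP.** Keep Arm A Visit 4 versus Arm B Visit 16. Beside it, prespecify the Visit 16/Visit 3 ratio within each Arm B participant as a supporting accumulation estimate: median ratio, 95% interval and signed-rank test on the log ratios. The signed-rank test named in the SAP is a paired test and suits this contrast. The between-arm comparison has no defined pairing, so its test needs to be reconciled, including for anyone who is in both arms.
4. **Reporting.** State that the ratio removes differences between groups but not drift between the two samples.

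**Cost:** a short amendment and a brief SAP addition. No extra visit, sample or assay is needed. The downside is that one existing visit loses its scheduling freedom, which also limits the choice of weekday for Visit 2.

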**ARM C (n=20; arm will close to enrollment once 10 people have completed study visits)**

**Visit 1 (screening):** Eligible MSM will provide informed consent, be questioned about their medical history, undergo a physical exam (conducted by a study clinician), a rapid HIV test, and a peripheral blood sample for a complete blood count, creatinine, coagulation test, and hepatitis B testing. Participants will then be asked to return within 1-6 weeks for visit 2.

**Visit 2:** Participants will return to the clinic to receive their first set of study drug for alternate week 2-1-1 dosing.. Participants will be instructed to provide documentation of all dosing with a time-stamped video or picture and provided with a calendar detailing when they should take the study drug. Participants will take the first 2 pills of their 2-1-1 dosing before leaving this visit.

**Visit 3-14:** Participants will return to do their weekly convenience sampling. Approximately 24 mL of blood will be drawn, urine sample, and a finger stick will be collected. A rapid HIV test will be completed at visits 6, 10 and 14 (once per month) along with optional hair samples. Participants will have urine and rectal STI testing at visit 10. An additional creatinine test will be done at visit 14. Participants will be provided with their medication at visits 5, 8, and 11.

**Visit 15:** Participants will return to the clinic to take their final dose of study drug in clinic. After the dose is taken, approximately 24mL of blood will be drawn, urine sample, and a finger stick will be collected.

**Visit 16:** Participants will return to the clinic 24 (+/- 2 hrs) hours after their last dose at visit 15. Approximately 24mL of blood will be drawn, urine sample, and a finger stick will be collected.

**Visit 17:** Participants will return to the clinic 2-5 days after their last dose at Visit 15. Approximately 24mL of blood will be drawn, urine sample, and a finger stick will be collected.

**Visit 18:** Participants will return to the clinic 7 (+/- 1 day) days after their last dose at visit 15. Approximately 24mL of blood will be drawn, urine sample, and a finger stick will be collected, along with an optional hair sample.

**Visit 19:** Participants will return to the clinic 14 days (+/- 1 day) after their last dose at visit 15. Approximately 24mL of blood will be drawn, urine sample, and a finger stick will be collected, along with an optional hair sample.

**Visit 20:** Participants will return to the clinic 21 (+/- 1 day) days after their last dose at visit 15. Approximately 24mL of blood will be drawn, urine sample, and a finger stick will be collected, along with an optional hair sample.

**Visit 21:** Participants will return to the clinic 28 days (+/- 1 day) after their last dose at visit 15. Approximately 24mL of blood will be drawn, urine sample, and a finger stick will be collected, along with an optional hair sample.

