## STUDY POPULATION

### **INCLUSION CRITERIA**

- 1) HIV-negative person, who was assigned male at birth, who reports sex with another man in the last year, and is in good general health.
- 2) Aged 18-59 years
- 3) Not currently taking PrEP and no plans to initiate during study
- 4) Not currently taking PEP
- 5) Consistent condom use and willing to use condoms for the duration of the study
- 6) Able to provide informed consent in English
- 7) No plans for relocation in the next 4 months
- 8) Willing to undergo peripheral blood, urine, finger stick, and optional hair sampling.
- 9) Willing to use study products as directed
- 10) Hepatitis B surface antigen (HBsAg) must be negative (screening lab test)
- 11) Creatinine clearance >60 ml/min

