**ARM D (n=20; arm will close to enrollment once 10 participants complete study visits)**

**Visit 1 (screening):** Eligible MSM will provide written informed consent, be questioned about their medical history, undergo a physical exam (conducted by a study clinician), a rapid HIV test, and a peripheral blood sample for creatinine and hepatitis B testing. Participants will then be asked to return within 1-6 weeks for visit 2.

**Visit 2:** Participants will return to the clinic to receive their first set of study drug for consecutive week 2-1-1 dosing; 8 doses of study drug for 2-1-1 dosing once per week on consecutive weeks followed by 2 consecutive weeks without dosing for 13 weeks. Participants will be instructed to provide documentation of all dosing with a time-stamped video or picture and provided with a calendar detailing when they should take the study drug. Participants will take the first 2 pills of their 2-1-1 dosing before leaving this visit.

**Visit 3-14:** Participants will return to do their weekly convenience sampling. Approximately 24 mL of blood will be drawn, urine sample, and a finger stick will be collected. A rapid HIV test will be completed at visits 6, 10 and 14 (once per month) along with optional hair samples. An additional creatinine test will be done at visit 14. Participants will be provided with their medication to follow this aforementioned dosing schedule at visits 5, 8, and 11.

**Visit 15:** Participants will return to the clinic to take their final dose of study drug in clinic. After the dose is taken, approximately 24mL of blood will be drawn, urine sample, and a finger stick will be collected.

**Visit 16:** Participants will return to the clinic 24 (+/- 2 hrs) hours after their last dose at visit 15. Approximately 24mL of blood will be drawn, urine sample, and a finger stick will be collected.

**Visit 17:** Participants will return to the clinic 2-5 days after their last dose at Visit 15. Approximately 24mL of blood will be drawn, urine sample, and a finger stick will be collected.

**Visit 18:** Participants will return to the clinic 7 (+/- 1 day) days after their last dose at visit 15. Approximately 24mL of blood will be drawn, urine sample, and a finger stick will be collected, along with an optional hair sample.

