**Visit 19:** Participants will return to the clinic 14 days (+/- 1 day) after their last dose at visit 15. Approximately 24mL of blood will be drawn, urine sample, and a finger stick will be collected, along with an optional hair sample.

**Visit 20:** Participants will return to the clinic 21 (+/- 1 day) days after their last dose at visit 15. Approximately 24mL of blood will be drawn, urine sample, and a finger stick will be collected, along with an optional hair sample.

**Visit 21:** Participants will return to the clinic 28 days (+/- 1 day) after their last dose at visit 15. Approximately 24mL of blood will be drawn, urine sample, and a finger stick will be collected, along with an optional hair sample.

*Biological specimens:*

Hair samples will be taken from those participants who are able to give a hair sample. 50-100 strands of hair will be taken using scissors at the above specified visits.

Biologic specimens collected after the screening visit will be transferred directly to CDC for measurement of study drug levels. Specimens will be labeled with a unique ID that only the Emory study team will be able to link to identifiable information. CDC personnel will not have access to identifiable information.

*Contingency visit:*

Attempts to ensure adherence to the study visits will be made with telephone and/or email reminders to the participant. However, if for example, screening laboratory results are lost or are inconclusive or if a participant has been unable to adhere to study protocol, he may be rescheduled for a future date where the above visit procedures will be performed. These additional visits will be scheduled within the above visit windows.

*Missed Visits:*

In all arms, up to 3 missed visits (~15% of all study visits) are allowed.

*Timing of procedures after dose:*

The procedures conducted after dose, particularly those less than 24 hours after dose, should occur as close to the scheduled time points as possible. Protocol deviations will be filed for visits that occur outside of the target windows identified above only if the visit is conducted more than 3 hours beyond the target window defined above for each arm and visit.

*Phone calls/retention contacts:*

While on study, periodic phone calls, texts, or email reminders will occur between study staff and participants to ensure proper retention and adherence to study protocol.

Statistical Analysis Plan

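### Arms C and D list no baseline study-drug test, so drug from recent pre-study PrEP or PEP use has no direct check; the early weekly levels are exposed most, the primary comparison only conditionally

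*Combined protocol and SAP*

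**What the plan says.** - **Visit 1, Arms A and B.** The screening blood covers creatinine and hepatitis B, "as well as testing for baseline levels of study drug".
- **Visit 1, Arm C.** The list is "a peripheral blood sample for a complete blood count, creatinine, coagulation test, and hepatitis B testing". No drug level appears.
- **Visit 1, Arm D.** The list is "a rapid HIV test, and a peripheral blood sample for creatinine and hepatitis B testing". Again there is no drug level.
- **Visit 2, all arms.** The first two pills are taken, and no specimen before them is listed. The gap from Visit 1 is 1 to 6 weeks.
- **Eligibility.** The inclusion criteria read "Not currently taking PrEP and no plans to initiate during study" and "Not currently taking PEP". Exclusion 4 adds intended use during the study. The 90-day medication look-back in exclusion 3 does not list PrEP or PEP. Exclusion 6 lets the investigator exclude for prior therapy, but gives no interval or drug level.
- **Re-entry (Study visits).** Participants may join a second arm at least 8 weeks after completing one. They "do not have to repeat the screening visit (visit 1) when starting another arm".
- **Specimen routing.** Under Biological specimens: "Biologic specimens collected after the screening visit will be transferred directly to CDC for measurement of study drug levels". The Lay Summary sends all collected specimens to CDC on the day of collection.
- **Analysis (Statistical Analysis Plan).** Dried-blood-spot TFV-DP at Visit 16 is compared between C and D as accumulation, with no baseline adjustment or exclusion. Other drug-level outcomes are exploratory.

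**The concern.** The study asks whether the marker builds up differently under different event-driven schedules. That reading assumes participants start from zero or from a known level. The plan obtains that level in two arms and omits it in the other two without giving a reason, although blood is drawn at the same visit.

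Someone who stopped daily PrEP shortly before screening meets the written criteria and could be dosed a week later. In C or D the first drug level would come at Visit 3, after dosing. It would be the sum of old and new drug, with no earlier value to separate them. At stake are the early part of the accumulation curves and, under narrower conditions, the C-versus-D comparison at Visit 16.

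**Working it through.** The plan states no half-life, effect size or variability, so there is no figure of its own to reproduce. The check below asks only whether the gap could matter.

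**From the documents:** screening gap of 7 to 42 days; 2-1-1 events of 2, 1 and 1 pills at 24-hour intervals; 13 dosing weeks; Visit 16 at 24 hours after the last dose; target of 10 completers per arm.

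**Assumed:** first-order decay with half-life *h* of 10, 17 or 30 days; earlier daily use at steady state, stopped the day before screening; Arm C dosed in weeks 1, 3, 5, 7, 9, 11, 13 and Arm D in weeks 1, 2, 5, 6, 9, 10, 13 (a reading of the schedules, 28 pills each). The last event then starts on day 84, its pills fall on days 84, 85 and 86, and Visit 16 is day 87.

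**Formulas** (units: the level from one pill)
- Level when daily use stops: S = 1/(1 − 2^(−1/h)).
- Residual after t days: S × 2^(−t/h). At day 7, t = 7 + 7 + 1 = 15 (1-week gap) or 7 + 42 + 1 = 50 (6-week gap). At Visit 16, t = 87 + 7 + 1 = 95 or 87 + 42 + 1 = 130.
- One event at day 7: 2×2^(−7/h) + 2^(−6/h) + 2^(−5/h).
- Arm C or D at Visit 16: sum of pills × 2^(−(87 − dose day)/h).

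**Results** (1-week gap / 6-week gap; ratios taken before rounding)

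| | h = 10 | h = 17 | h = 30 |
|---|---|---|---|
| S | 14.93 | 25.03 | 43.78 |
| One event, day 7 | 2.60 | 3.10 | 3.46 |
| Residual, day 7 | 5.28 / 0.47 | 13.58 / 3.26 | 30.96 / 13.79 |
| Residual ÷ one event | 2.0 / 0.2 | 4.4 / 1.05 | 8.9 / 4.0 |
| Arm C, Visit 16 | 5.51 | 8.24 | 12.31 |
| Arm D, Visit 16 | 4.93 | 7.51 | 11.58 |
| C − D, % of C | 10.5 | 8.8 | 6.0 |
| Residual at Visit 16, % of C | 0.4 / 0.0 | 6.3 / 1.5 | 39.6 / 17.6 |

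**From one person to the arm.** I simulated 10 per arm, lognormal levels with log-scale SD 0.3 (assumed), no true difference, a rank-sum test at 0.05, and the 1-week-gap residual added in one arm.
- One affected person: the arm median rises by 0.6 to 0.7% at h = 17 and about 3.6% at h = 30. The rejection rate stays at about 4%, as it is without contamination.
- Three affected of ten, all in one arm: the median rises by about 2% at h = 17, with the rejection rate essentially unchanged (4.5% to 4.6%). At h = 30 it rises by about 12%, and the rejection rate goes from about 4% to about 8%.

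**Re-entrants.** The last sample is 28 days after the last dose and the gap is at least 56 days, so about 84 days pass off drug. The share left is 2^(−84/h): 0.3%, 3.3% and 14% of the level at the last dose for h = 10, 17 and 30.

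**The case against.** Several points on the other side stand.

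- **The primary pairs are internally alike.** A is compared with B (both tested) and C with D (neither tested). A reader might infer that C versus D is biased. The documents do not support that: bias needs unequal past use between the two arms. Sequential assignment and 10 completers per arm make imbalance possible, but nothing shows it, and its direction is unknown.
- **The Visit 16 percentages describe one extreme individual.** Setting one person's 18 to 40% beside an arm difference of 6 to 10.5% does not compare like with like. A median and a rank test resist one high value, as the simulation shows.
- **Large residuals would often be visible.** C and D are sampled weekly from Visit 3, so a level several times that of one event, falling over time, would stand out. The residuals that stay hidden are the smaller ones. This is indirect evidence, though, and gives no rule for handling such a person.
- **Eligibility has other filters.** Medical history is taken, the target group is low-risk men not wanting daily PrEP, and exclusion 6 allows discretion. These make the worst case uncommon, but none is a look-back.
- **The specimen sentence is not exclusive.** A reader might infer that the A and B baseline samples are never assayed. The sentence does not say only later specimens go to CDC, and the Lay Summary sends all of them. The two need aligning; nothing more follows.
- **Re-entry carry-over is limited** by the 8-week gap, and a final level from the earlier arm is scheduled.

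The Design section also says in general terms that blood is collected during visits. That does not supply a baseline: the Visit 2 text lists no sample, and nothing places one before the pills.

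**Conclusion.** The gap is real. Two of four arms lack a baseline drug measurement that the other two have, and neither Visit 2 nor the eligibility criteria fills it. The main consequence is for the exploratory early weekly levels in C and D. There, one recent daily user's residual at day 7 would be 0.2 to 8.9 times one event's level, across assumed half-lives of 10 to 30 days and screening gaps of 1 to 6 weeks.

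For the primary C-versus-D comparison the risk is conditional. It is negligible at 10 days and small at 17. It becomes material only with a half-life near the long end and several recent users in the same arm. The stronger statement, that the primary result is contaminated, is not supported. All sizes rest on the assumed half-life and on steady-state daily use stopped the day before screening. The number of recent users is unknown, and the missing test is what would show it. The change is worth making because it is cheap and removes the doubt.

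**What to change.** - **Visit 1, Arms C and D:** add the Arm A wording ("as well as testing for baseline levels of study drug") to the blood already drawn.
- **Biological specimens:** align the sentence with the Lay Summary so that screening samples are expressly covered.
- **Re-entrants:** use the last level measured in the earlier arm (Visit 9 or Visit 21) as the baseline. It precedes re-entry by at least 8 weeks, so it is an upper bound on carry-over if no other drug was taken.
- **Statistical Analysis Plan:** add a sensitivity analysis that repeats C versus D at Visit 16, and the weekly curves, without participants who had quantifiable drug before the first dose.

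If screening in C or D is already finished, assay any stored screening blood. Failing that, report past PrEP and PEP use where it was recorded.

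Cost: one assay per participant in C and D on an existing draw, a few sentences of text, and possibly a few participants set aside in the sensitivity analysis. The primary analysis set does not change.
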